## **8.2 Changes to Protocol, Protocol Deviations and Protocol Amendments**

### **8.2.1 Changes to Protocol**

The Investigator should not implement any deviation from, or changes to the protocol without agreement by the sponsor and prior review and documented approval/favorable opinion from the IRB of an amendment, except where necessary to eliminate an immediate hazard(s) to study subjects, or when the change(s) involves only logistical or administrative aspects of the study (e.g., change in CRA(s), change of telephone number(s)). In the event of an emergency situation, the Investigator must notify the CRA or TMC immediately. A full written report of the situation must be forwarded to the IRB who approved the original protocol and TMC within 10 working days of the event.

### 8.2.2 Protocol Deviations

The Investigator agrees to conduct the study in accordance with this protocol; however, protocol deviations may occur during the course of the study. Protocol deviations are events occurring during the conduct of the study which are not in compliance with the protocol and for which an amendment has not been granted. Protocol deviations can be committed by the Sponsor, the PI, or the study subject. A deviation can be identified by a number of sources. Potential sources include but are not limited to: a member of the PI's staff, the CRA during monitoring visits, or a member of the data management or statistical groups when entering or analyzing data. The PI or PI's representative are encouraged to contact the CRA or TMC as soon as possible upon observing a protocol deviation. Regardless of the source, it is crucial to document the deviation and record all corrective actions. Protocol deviations will be reported in the final report.

The process for capturing deviations will be detailed in the monitoring plan. The process will require that documentation describe the deviation, and appropriate actions taken and will be included in the study file for the respective PI and subject. The study site representative will be advised to record the deviation and relevant discussion with the Sponsor about the deviation in the subject's source documentation.

Protocol deviations affecting the scientific soundness of the study or the rights, safety, or welfare of the subjects, will be reported by the PI, as required by the IRB.

Protocol deviations will be summarized and grouped into relevant categories for analysis and may include, but are not limited to, subjects who:

- Entered the study although they did not satisfy the eligibility criteria;
- Completed incorrect version of PROMIS based on age of subject
- Did not return to protective weight-bearing activities by 3 weeks (+3 days);
- Received Lapiplasty® Procedure (or other hallux valgus procedures) on contralateral foot less than 6 months after initial index procedure; or
- Developed withdrawal criteria during the study but were not removed from study participation.

### 8.2.3 Protocol Amendments

If it becomes necessary to amend the protocol, then the nature of the amendment will be agreed upon by the Sponsor and the Principal Investigator(s) and this will be recorded with a justification for the amendment. The appropriate IRBs will be informed of amendments prior to implementation of the change.

## 9.0 STATISTICAL CONSIDERATIONS

In this prospective, single arm, non-comparative study, the analyses will be mainly descriptive. Inferential statistical methods, if applied, will be utilized to highlight the data aspect of interest. Unless otherwise specified, statistical tests will be 2-sided using a 0.05 statistical significance level. Corresponding 95% confidence intervals will be presented as appropriate. No corrections for multiple

testing will be applied. Full details of all statistical issues and planned statistical analyses will be specified in a separate statistical analysis plan, which will be finalized prior to the locking of the study database.

### **9.1 Analysis of the Conduct of the Study**

The number of subjects enrolled in the study will be tabulated by the center. A subject disposition table will be tabulated, and will include the number of subjects enrolled, treated, and completing the study. Subject discontinuations and reasons for discontinuation will be summarized.

### **9.2 Sample Size**

There is no formal sample size calculation as this is a single arm study and is descriptive in nature. A sample size of 200 patients is chosen, ensuring the feasibility of the study as clinical findings suggest that the bunion recurrence rate after the Lapiplasty® Procedure is low.

### **9.3 Analysis Population**

Intent-to-Treat (ITT) population: The ITT population is defined as all enrolled subjects who were treated with the Lapiplasty® Procedure using the Mini-Incision™ System.

Per-Protocol (PP) Population: The per-protocol population is defined as all enrolled subjects who were treated with the Lapiplasty® Procedure using the Mini-Incision™ System who did not experience a major protocol violation. Major protocol violations include, but are not limited to, subjects who:

- Entered the study although they did not satisfy the eligibility criteria;
- Completed incorrect version of PROMIS based on age of subject;
- Did not return to protective weight-bearing activities by 3 weeks (+3 days);
- Received Lapiplasty® Procedure (or other hallux valgus procedures) on contralateral foot less than 6 months after initial index procedure; or
- Developed withdrawal criteria during the study but were not removed from study participation.

### **9.4 Analysis of Study Endpoints**

All analyses of efficacy, safety, and health economic endpoints will use the ITT population. If the PP and ITT populations differ considerably, the PP population may be used for supportive efficacy analyses to evaluate the influence of major protocol violations on key endpoints.

### **9.5 Missing Data**

Efficacy and health economic analyses will be based on available data, without imputation for missing values. For the Quality of Life outcomes, missing data will be handled as specified in the PROMIS-29, PROMIS-25 and MOXFQ scoring manuals. For safety analyses, missing event dates will be imputed as follows:

- If only month and year are reported, then day is assigned as the 15th of the month

- If only year is reported, then month and day is assigned as July 1st

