6.3 Missing Data

Effectiveness and health economic analyses will be based on available data, without imputation for missing values. For Quality of Life outcomes (MOxFQ and PROMIS-29/PROMIS-25), missing data will be handled as specified in the Derived Variables section. For safety analyses, missing event dates will be imputed as follows:

- If only month and year are reported, then day is assigned as the 15th of the month
- If only year is reported, then month and day is assigned as July 1st

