6.4.4 MOxFAQ

The Manchester Oxford Foot Questionnaire (MOxFAQ)⁷ is a 16 item, subject-reported outcome measure designed for use with individuals who are undergoing foot or ankle surgery. Each of the 16 questions on the MOxFAQ is scored in the same direction with the score increasing as the reported health status becomes worse. Scores for each domain of the MOxFAQ are calculated as the sum of each individual item score. In each case, this is expressed on a metric of 0 – 100 (where a higher score represents greater severity) and will be calculated as (actual score/maximum possible domain score)*100. If a single item within any domain is unanswered, the mean value from the respondent's other item responses (series mean) within that domain will be used for the missing response. If more than one item within any domain is unanswered, then all item responses for that domain will be set to missing.

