6.4.5 PROMIS-29/PROMIS-25

The PROMIS profile instruments⁶ are a collection of short forms containing a fixed number of items. The PROMIS-29 is intended for adults (aged 18+ years) and assesses seven PROMIS domains (Depression, Anxiety, Physical Function, Pain Interference, Fatigue, Sleep Disturbance, and Ability to Participate in Social Roles and Activities). The PROMIS-25 is intended for children (aged less than 18 years) and assesses six PROMIS domains (Depressive Symptoms, Anxiety, Physical Function-Mobility, Pain Interference, Fatigue, and Peer Relationships). Each domain has 4 items, with each item having five response options ranging in value from 1 to 5. A separate pain intensity item is also assessed and has eleven response options ranging in value from 0 to 10. All domains are assessed over the past seven days except for Physical Function (PROMIS-29) which has no timeframe specified.

A raw score is created from each short form that makes up the profile. To find the total raw score for a short form with all questions answered, sum the values of the response to each question within each domain. To translate the total raw score into a T-score for each short form for each participant, a PROMIS score conversion table is used. The T-score rescales the raw score into a standardized score with a mean of 50 and a standard deviation (SD) of 10. The standardized T-score is reported as the final score for each participant.

If an item in a short form is unanswered, then the total raw score and T-score for that short form will not be calculated.

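### SAP 6.4.5 drops a four-item PROMIS domain for one blank item while SAP 6.4.4 keeps a MOxFQ domain with one blank, and the SAP does not tie its PROMIS rule to the scoring manual the protocol names

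*Protocol*

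**What the plan says.** The two documents name different sources for the same rule. Protocol 9.5: "For the Quality of Life outcomes, missing data will be handled as specified in the PROMIS-29, PROMIS-25 and MOXFQ scoring manuals". SAP 6.3, on the same outcomes: "missing data will be handled as specified in the Derived Variables section".

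Within the SAP's derived-variable rules, the two instruments are treated differently.

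- **PROMIS (SAP 6.4.5).** "Each domain has 4 items, with each item having five response options ranging in value from 1 to 5". Scoring is by summing and look-up: "To translate the total raw score into a T-score for each short form for each participant, a PROMIS score conversion table is used". For blanks: "If an item in a short form is unanswered, then the total raw score and T-score for that short form will not be calculated".
- **MOxFQ (SAP 6.4.4).** The rule begins "If a single item within any domain is unanswered, the mean value from the" and goes on to fill the gap with the average of that person's remaining answers in the domain. Only beyond one blank is the domain lost: "If more than one item within any domain is unanswered, then all item responses for that domain will be set to missing".

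Both instruments serve one secondary endpoint, change from baseline in quality of life at 6, 12 and 24 months. SAP Tables 22 and 23 report PROMIS for adults and for pediatric subjects, and SAP section 7 applies two-sided t-tests to changes from baseline.

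**The concern.** When one of four PROMIS items is blank, three valid answers are thrown away. The endpoint is a change, so a blank at baseline removes that domain from every later comparison, and a blank at follow-up removes it from that visit's comparison. For the same endpoint, the SAP accepts one blank per domain on the MOxFQ.

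Nothing in the SAP explains the difference. Section 6.4.5 does not say that its rule comes from the PROMIS manual, and the SAP's reference list contains no PROMIS or MOxFQ manual. The superscript given for PROMIS leads to a study of sesamoid reduction after surgery. Protocol 9.8 expects the SAP to give reasons where it changes the planned analysis. From the two documents alone, a reader cannot tell whether the protocol's instruction has been carried out or replaced.

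At stake is precision in Tables 22 and 23. The pediatric table, probably the smaller of the two, can least spare the data. The primary endpoint is not affected.

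**Working it through.** The documents state no figure for item non-response, quality-of-life precision or power, so there is no published number to reproduce. The calculation below is an illustration under a stated assumption.

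**Inputs**
- Items per PROMIS domain: 4 (SAP 6.4.5).
- Visits needed for a change score: 2 (baseline and the follow-up visit).
- Planned number of subjects: 200 (Protocol 9.2), used only to scale the percentages.
- Probability q that an item is blank: **assumed**, independent across items and visits. Values shown are 0.5%, 1%, 2% and, as a high case, 5%.

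**Formulas**
- Domain scored at one visit under SAP 6.4.5: A = (1−q)^4.
- Domain scored at one visit if one blank is tolerated, as for the MOxFQ: B = (1−q)^4 + 4q(1−q)^3.
- Change scores lost per domain: 1 − A² = 1 − (1−q)^8 under the SAP rule, and 1 − B² under the tolerant rule.
- Ratio of confidence-interval widths, if mean and SD are unaffected: √(B²/A²) = B/A.
- Share of lost domain-visit scores with exactly one blank: 4q(1−q)^3 / (1 − A).

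**Worked case, q = 1%**
- A = 0.99^4 = 0.9606, A² = 0.9227, so 7.7% is lost.
- B = 0.9606 + 0.0388 = 0.9994, B² = 0.9988, so 0.12% is lost.
- B/A = 0.9994/0.9606 = 1.040, an interval about 4% wider under the SAP rule.

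| q (assumed) | Lost, SAP rule | Lost, one blank tolerated | Per 200 subjects | Interval wider by | Lost domain-visit scores with exactly one blank |
|---|---|---|---|---|---|
| 0.5% | 3.9% | 0.03% | 7.9 vs 0.1 | 2% | 99% |
| 1% | 7.7% | 0.12% | 15.5 vs 0.2 | 4% | 98.5% |
| 2% | 14.9% | 0.47% | 29.8 vs 0.9 | 8% | 97% |
| 5% | 33.7% | 2.8% | 67.3 vs 5.6 | 21% | 92% |

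The per-200 column assumes that every subject attends both visits. It scales down with attrition and is shared between the adult and pediatric tables.

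**Do the printed items point to bias?** The adult chores item offers a response for people who cannot do the task, so inability alone is no reason to leave it blank. The pediatric schoolwork item belongs to Fatigue, not to physical function. The forms therefore do not show that subjects with poor function would be selectively dropped from the function domain.

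**The case against.** The case for leaving the SAP as it stands has several parts.

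- **The manuals are not in the documents.** A reader might infer that the SAP contradicts the protocol, or that scores are lost for no reason. Neither follows. If the PROMIS manual requires complete forms for the conversion-table route, SAP 6.4.5 does exactly what Protocol 9.5 asks. This part stands in full.
- **Different rules for different instruments are not in themselves an error.** Protocol 9.5 names separate manuals. MOxFQ domains are a simple percentage of the maximum, where mean substitution is easy, while the PROMIS table takes a complete raw sum. This stands as an explanation the SAP could give, but the SAP does not give it.
- **Prorating is imputation, and SAP 6.3 says:** "Effectiveness and health economic analyses will be based on available data, without imputation for missing values". This carries less weight. The next sentence of 6.3 makes a separate provision for quality of life, and 6.4.4 already fills single MOxFQ items. Using three answers in hand also sits well with an available-data principle.
- **The size is assumed.** This stands. Independence matters too: if blanks cluster in a few subjects, fewer change scores are lost at the same average rate, and a one-blank tolerance recovers a smaller share of them. The forms ask for one box per row, and Inclusion criterion 6 requires the ability to complete questionnaires, both of which argue for a low rate.
- **The loss will be visible.** SAP section 7 reports n and annotates tables with the relevant population. That shows how many scores are missing, but not how many were lost to a single blank item.

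**Conclusion.** The point holds in a limited form. SAP 6.4.5 states a clear rule that discards three observed answers when a fourth is blank. It is stricter than the MOxFQ rule for the same endpoint, and it is neither attributed to the manual named in Protocol 9.5 nor justified. Whether it departs from that manual cannot be determined from the documents.

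The cost is precision. Under independent blanks at 0.5% to 2% per item, 3.9% to 14.9% of change scores per domain are lost and intervals are about 2% to 8% wider than with one blank tolerated. Calling this modest depends on the rate being in that range; at 5% the loss would be a third. The documents give no rate.

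A reader might go further and infer that the PROMIS results will be biased, with subjects of poor function removed from the function domain. The printed items do not support that, and no bias is demonstrated. The endpoint is secondary and the study is descriptive, without a formal sample size calculation.

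**What to change.** Before database lock:

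1. Check SAP 6.4.5 against the PROMIS manual that Protocol 9.5 names, and cite the manual correctly in the SAP references.
2. Unless the manual forbids it, replace the last sentence of 6.4.5. A domain with three of four items answered is scored from those answers, either by IRT response-pattern scoring or by prorating the raw sum (sum × 4/3, with the rounding stated) before T-score conversion. A domain with two or more blanks is set to missing. The same rule applies at baseline and at every follow-up visit.
3. If the manual does require complete items, keep the present rule and say that it is the manual's.
4. In either case, report for each domain and visit how many scores were derived from three items and how many were lost to partial non-response.
5. Make Protocol 9.5 and SAP 6.3 point to the same rule.

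The cost is a sentence and a reference in the SAP, a matching line in the protocol, and a few lines of code. The downside is a small approximation error in the few scores built from three answers.

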## **9.6 Interim Analyses**

Interim analyses will be performed during the study according to patient enrollment and availability of data of interest. Interim analyses will be used to provide early information about the safety and efficacy of the procedure and may be used for internal decision making, hypothesis generation, abstraction/publication for major orthopedic conferences, or other purposes, as applicable. Interim analyses will follow the methods in the statistical analysis plan.

## **9.7 Safety Analyses**

AEs related to the Lapiplasty® Procedure and the Lapiplasty® devices will be reported on the eCRF. These AEs will be listed and descriptively summarized for all subjects. No formal statistical hypothesis will be tested.

## **9.8 Detailed Analysis Plan**

Prior to database closure, a detailed statistical analysis plan will be finalized to completely specify the statistical procedures to be applied to the data by the statistician who will conduct the analysis. The plan will amplify the methods discussed in this protocol, will address any protocol changes that would affect the analysis, and will provide a rationale for any changes to the analysis.

## **10.0 SAFETY MONITORING**

Subject safety will be monitored throughout the course of this study by monitoring for Adverse Events and Product Complaints related to the Lapiplasty® Mini-Incision™ System Implants, the Lapiplasty® Mini-Incision™ Precision Instrument Set. The Lapiplasty® devices used during the index procedure for the clinical study have been cleared for marketing by the FDA and are being used within the current labeling and indications for use. Any event that occurs that may have caused or contributed to a death or serious injury or that indicates that the devices have malfunctioned and would be likely to cause or contribute to a death or serious injury if the malfunction were to recur will be reported in compliance with 21 CFR Part 803.

In addition to general surgical risks (risks associated with anesthesia, infection, damage to nerves and blood vessels, and bleeding or blood clots), additional risks specifically associated with the Lapiplasty® System Implants are as follows:

- Infection or adverse reaction for a foreign body;
- Pain, discomfort, or abnormal sensations due to the presence of the implant;
- Loosening, bending, cracking or fracture of the components or loss of fixation of bone attributable to nonunion, osteoporosis, markedly unstable comminuted fractures;
- Loss of anatomic position with nonunion or malunion with rotation or angulation;
- Migration of the implant, loosening of the implant;
- Delayed correction in alignment;
- Decrease in bone density due to stress shielding;

- Bursitis;
- Additional surgery if the device is not placed in the correct position.

Metallic implants can loosen, fracture, corrode, migrate, cause pain, or stress shield bone even after a fracture is healed. If any of these complications occur, the surgeon must make the final decision on implant removal.

There may also be other risks that are unforeseen at this time. The complete Risk/Benefit Assessment is found in **Appendix 5**.

## **10.1 Adverse Events**

### **10.1.1 Definition of an Adverse Event**

Adverse Event (AE): any undesirable clinical occurrence or change from a patient's baseline (pre-index procedure) condition, whether it is device related or not.

Adverse Event Identification: a condition that is one of the following:

- a. A unique symptom or event that is a change from the subject's baseline status
- b. A series of symptoms or events that can be categorized as a single entity
- c. A specific diagnosis responsible for a clinical change
- d. A worsening or exacerbation of a pre-existing condition

## **10.2 Serious Adverse Events**

### **10.2.1 Definition of a Serious Adverse Event**

Serious Adverse Event (SAE): any adverse event is considered serious if it results in death, is life threatening, requires hospitalization (initial or prolonged), results in disability or permanent damage, causes congenital anomaly/birth defect, requires intervention to prevent impairment or damage, or other serious (important medical events) which may jeopardize the subject and may require medical or surgical intervention to prevent one of the above outcomes.

Note: "Death" should not be reported as an adverse event. The cause of death should be reported as an adverse event. The only exception is "Sudden Death" when the cause is unknown.

### **10.2.2 Subject Death**

Subject death during the investigation must be reported by the Investigator (or designee) by completing the Study Exit eCRF in the database along with the cause of death. The electronic Adverse Event Form is necessary if the event was related to the Lapiplasty® devices or placement of the device. In addition, subject death must be reported to the IRB in accordance with IRB requirements.

### **10.2.3 Adverse Event Classification**

The investigator is required to provide:

- Time interval of the event – The time interval of the occurrence of the adverse event should be assessed in relationship to timing of the index procedure (Lapiplasty® Procedure)
- Date of event onset and outcome of the event, or date of death

- Severity of the event – (Mild, Moderate, Severe)
- Action taken for medical management of the event
- Relationship of the event – it is the PI's responsibility to assess the relationship of an AE and provide primary cause. Events will be categorized by relationship to the Lapiplasty® System Implants, the Lapiplasty® System Reusable Instruments, or the index procedure (Lapiplasty® Procedure).
- Adverse events will be assessed to determine if the event meets the definition of a serious adverse event.

#### 10.2.4 Reporting Adverse and Serious Adverse Events

The investigator (or designee) will record all AEs (both serious and non-serious and regardless of relationship) in the source documents. The Investigator at each participating site is responsible for reporting AEs and SAEs to TMC only when they are related to the Lapiplasty® Procedure, the Lapiplasty® Mini-Incision™ System Implants and Lapiplasty® Mini-Incision™ Precision Instrument Set. AEs related to the Lapiplasty® Procedure or Lapiplasty® devices will be reported on the eCRF. The CRF allows the investigator to indicate whether an adverse event is related to the Lapiplasty® System devices or Lapiplasty® Procedure (index procedure).

- Use a separate Adverse Event Form to document each event
- The Adverse Event Form must be electronically signed by the Investigator

*Note: It is the responsibility of the Investigator to inform their IRB of SAEs as required by their IRB procedures and in conformance with FDA requirements.*

For the purposes of this study, the following adverse events are not considered reportable (recorded on eCRF) because they are normally expected to occur in conjunction with surgical treatment for hallux valgus procedures or are associated with customary and standard care of patients undergoing surgical treatment of hallux valgus or other protocol approved and acceptable concomitant procedures. If any of these events are **beyond what is normally expected** after the Lapiplasty® Procedure, they should be reported as AEs. However, the decision to report any AEs is ultimately the decision and responsibility of PI.

- Post-operative pain/post-procedure pain
- Minor, localized tenderness, swelling, induration, oozing, etc. at surgical site
- Temporary numbness or tingling at surgical site
- Elevated White Blood Cell count without signs and symptoms of infection
- Stiffness/weakness of joint

*Note: Subjects will undergo general anesthesia and therefore will also be subject to general anesthesia-associated complications and morbidity. These are also not considered reportable (recorded on eCRF) adverse events.*

Any pre-planned surgical procedures

- Any pre-planned surgical foot procedures at the time of informed consent will not be considered reportable (recorded on eCRF) adverse events (whether hospitalization is required or not).

All Serious Adverse Events that are related to the index procedure or the Lapiplasty® devices must be reported by the Investigator by submitting the AE eCRF to TMC within 10 days of becoming aware of

the AE and recorded on the Serious Adverse Event Source Document Collection Form. Any event determined by the Investigator to be life threatening or to have led to death should be reported within 24 hours.

The Investigator shall send a written report including a narrative description of the SAE to TMC within three (3) working days of the initial report. The Investigator should follow all unresolved SAEs until the events are resolved, or the subject has exited the study, or the AE is otherwise explained.

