## STUDY ADMINISTRATIVE STRUCTURE

This study is sponsored by Treace Medical Concepts, Inc. and will be conducted in the US, under a single protocol approved by an IRB for each site prior to implementation at the study site.

The Principal Investigators (PI) at the study sites are required to be either a DPM or MD/DO qualified by education, experience and training to assume responsibility for the conduct of this study. Individual centers and investigators are selected based on their prior experience with the Lapiplasty® Procedure and use of the Lapiplasty® Mini-Incision™ System.

An Electronic Data Capture (EDC) system will be utilized by study site personnel to transfer study data from source records (medical records and/or source document worksheets) onto common electronic case report forms (eCRFs). The EDC system is a web-based, secure electronic software and is compliant with national and international GCP data protection/data privacy and electronic record/electronic signature (e.g., 21 CFR Part 11) regulatory requirements.

Serious Adverse Events (SAEs) and product quality problems (for products used during the index procedure), including potential and actual product use errors suspected to be associated with the use of a Food and Drug Administration (FDA) regulated drug, biologic, medical device or dietary supplement used during the course of this study will be reported by the PI to applicable authorities including the: 1) Sponsor (TMC); 2) IRB; 3) respective manufacturer(s); and/or 4) FDA via MedWatch Online Voluntary Reporting Process or Medical Device Reporting (MDR) as appropriate.

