7.3.1 Adverse Events

Adverse events (AEs) related to the Lapiplasty® Procedure and the Lapiplasty® devices that are captured at the time of the index procedure and up until the time of the last study visit will be included in the analysis. Number and proportion of subjects with at least one AE, total number of AEs, and number of subjects with at least one AE by AE type will be summarized using the reported AE term, and the following summaries will be generated:

- All AEs
- Serious AEs (SAEs)
- AEs leading to death
- AEs leading to device removal/surgical intervention
- AEs leading to study discontinuation

Subject level listings will also be produced and will include subject ID, age, sex, AE term, AE description, AE start and end dates, action taken, outcome, primary relationship, secondary relationship, and SAE (y/n).

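### Protocol sections 10.2.2 and 10.2.4 disagree on which serious and fatal events go on the AE eCRF, so some can fail to reach SAP Tables 18 and 19

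*Protocol*

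**What the plan says.** **Anaesthesia.** Protocol section 10.2.4 lists expected post-operative events, such as pain and minor swelling, that need not go on the eCRF. Before that list it adds that if such events exceed normal expectation, "they should be reported as AEs. However, the decision to report any AEs is ultimately the decision and responsibility of PI". After the list a separate note says that subjects "will also be subject to general anesthesia-associated complications and morbidity. These are also not considered reportable (recorded on eCRF) adverse events".

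**Related SAEs.** The last part of section 10.2.4 says: "All Serious Adverse Events that are related to the index procedure or the Lapiplasty® devices must be reported by the Investigator". The vehicle is the AE eCRF, within 10 days. Events judged life-threatening or fatal are to be reported within 24 hours.

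**Deaths.** Section 10.2.2 puts every death and its cause on the Study Exit eCRF and then says: "The electronic Adverse Event Form is necessary if the event was related to the Lapiplasty® devices or placement of the device".

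**Analysis.** SAP section 7.3.1 includes captured AEs related to the procedure and devices. Its planned summaries include SAEs and "AEs leading to death", which become Tables 18 and 19, both on the ITT population.

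**The concern.** The SAE and fatal-AE tables can show only what reaches the AE form. If two parts of the safety section give different answers about whether a form is due, two sites can handle the same event differently and both can point to the protocol. The events concerned are the most serious ones around surgery: a serious anaesthesia complication, or a death from a surgical complication unconnected with the implant. Any resulting error goes one way, towards fewer SAEs and fewer fatal AEs. In a single-arm study whose safety results are purely descriptive, nothing later in the analysis would reveal the gap.

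**Working it through.** The plan has no figure to reproduce. Protocol section 9.2 says there is no formal sample size calculation, and neither document gives a rate for serious anaesthesia events or deaths. The check sets the texts side by side.

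**Step 1: a serious anaesthesia complication**
- *Anaesthesia note, 10.2.4:* off the eCRF, with no limit by seriousness, severity or relatedness.
- *Override, 10.2.4:* stands before the bulleted list and speaks of the listed events. The note comes after the list. The text does not say whether the override reaches it.
- *SAE paragraph, 10.2.4:* all SAEs related to the index procedure or devices go on the AE eCRF, with no anaesthesia exception.
- *Section 7.2 (Visit 2):* the AE assessment is to include intra-operative procedural complications.

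If the investigator judges the event related to the index procedure, the note says to leave it off and the SAE paragraph says to file it. If it is judged unrelated, there is no conflict, because only related events are in scope. Which case applies is itself unclear. Section 5.1 defines the index procedure narrowly, as use of the Mini-Incision System only, while sections 10.2.3 and 10.2.4 treat it as the same thing as the Lapiplasty Procedure.

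**Step 2: a death**
- *10.2.2:* AE form if related to the devices or their placement.
- *10.2.3:* relationship is classified under three headings: implants, reusable instruments and index procedure.
- *SAE paragraph, 10.2.4:* index procedure or devices.

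Take a fatal post-operative blood clot, a risk that section 10.0 lists among general surgical risks. Suppose it is judged related to the procedure but not to the device or its placement. Under the SAE paragraph it needs the AE eCRF. Under 10.2.2 taken alone, the Study Exit form is all that is asked for.

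**Step 3: the route to the tables**
- SAP 7.3.1 starts from captured related AEs. No SAP step compares them with deaths on the Study Exit form, so a death recorded only there has no route into Table 19.
- Tables 17 to 19 use the ITT population, which SAP 6.2.1 limits to treated subjects. SAP 7.1.1 counts in the disposition table subjects who were anaesthetised but not treated. An anaesthesia SAE in such a subject stays outside Tables 17 to 19 even if it is on the eCRF.

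**Step 4: scale of one omission**

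Assume all 200 planned subjects are treated, and use exact (Clopper-Pearson) 95% intervals. For zero events the upper limit is 1 − 0.025^(1/200) = 1.83%.

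| Subjects with an event | Proportion | Exact 95% CI |
|---|---|---|
| 0 | 0/200 = 0% | 0 to 1.83% |
| 1 | 1/200 = 0.5% | 0.01 to 2.75% |
| 2 | 2/200 = 1.0% | 0.12 to 3.57% |

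This shows what each missing subject does to a table. It does not say how many to expect.

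**The case against.** The best reply is that this is loose wording and not a loss of data. The SAE paragraph still applies, the investigator may report any AE, and every death with its cause is on the Study Exit eCRF. The study is post-market, its devices are cleared, and it deliberately collects related events only. Placement of the device also covers much of the index procedure as section 5.1 defines it, so the gap for deaths is narrow.

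Much of that stands, and it rules out several stronger readings that a reader might infer:

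- **That these events never reach the tables.** A site following the SAE paragraph files the form. The supportable statement is that capture depends on which text is followed.
- **That 10.2.2 excuses an AE form for other deaths.** It says when the form is needed. It does not say the form is unnecessary otherwise.
- **That 10.2.2 clearly contradicts 10.2.1.** The sentence "The cause of death should be reported as an adverse event" sits in a note on what term to use when a subject dies. It can be read as a naming rule.
- **That the Study Administrative Structure section conflicts with the exemption.** It covers SAEs and product problems "suspected to be associated with the use of a Food and Drug Administration (FDA) regulated drug, biologic, medical device or dietary supplement" and sends them to the sponsor and other bodies as appropriate. It does not mention the AE eCRF, and the exemption concerns only eCRF recording.
- **That the hospital-readmission endpoint is affected.** Nothing derives readmission from AE forms. Health economic outcomes have their own row in the Schedule of Assessments, and its footnote points to an endpoint list that includes readmission.

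What does not stand is the use of investigator discretion as a safeguard. It allows a form without requiring one. The narrow definition in section 5.1 does not help either: if anaesthesia falls outside the index procedure, the 10-day SAE rule may not reach those events at all.

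**Conclusion.** The concern holds as an internal contradiction with a possible effect on two safety tables. Section 10.2.4 exempts anaesthesia complications without a seriousness limit and also requires all index-procedure-related SAEs on the AE eCRF. Section 10.2.2 uses a narrower trigger for deaths than the SAE paragraph and the relationship categories in 10.2.3. The SAP has no step that would repair a missing form. Serious or fatal related events can therefore be absent from Tables 18 and 19, though not deaths from the database.

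The number of events affected cannot be estimated from the documents. Each omitted subject lowers a table entry by 0.5 percentage points if 200 are treated, and a single one can decide whether a table reads zero. The conclusion rests on two assumptions: that at least one such event occurs and is judged related, and that some sites follow the anaesthesia note or section 10.2.2 in preference to the SAE paragraph.

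**What to change.** Reconcile the texts:

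1. **Protocol 10.2.4.** State that the anaesthesia exemption does not cover events meeting the SAE definition. Say also whether general anaesthesia given for the index procedure counts as procedure-related, since section 5.1 could otherwise remove the same events again.
2. **Protocol 10.2.2.** Use the same trigger as the SAE paragraph for the AE form after a death: related to the index procedure or the devices. Requiring a form for every death would go beyond the study's related-only scope and is not needed.
3. **SAP 7.3.1.** State that deaths on the Study Exit eCRF are reconciled with Table 19 before the tables are final. Report serious events in subjects anaesthetised but not treated separately, since they are outside the ITT tables.

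The cost is a few sentences in each document, a few extra AE forms, and possibly a slightly higher SAE count.
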